Enrollment of subjects within the original study framework was put on hold beginning on March 16, 2020 due to the necessary hospital response to prevent further spread of COVID-19 and to maximize resources to treat hospitalized patients. Adding a second control group where all variables except for biologic and survey data will allow comparison of three different care conditions, intervention plus usual care, usual care only and usual care only during a pandemic. Usual care in terms of study visit timing, number, and length may be different than pre-pandemic care paradigms due to staff redeployment and restructuring are care areas to support care during a disaster.

3. Study Procedures

- a. Study design, including the sequence and timing of study procedures (distinguish research procedures from those that are part of routine care).

This pilot study uses a randomized parallel group design to determine the difference in the expression of pro- and anti-inflammatory cytokines in response to this specific exercise intervention plus usual care versus usual care only. Patients will be enrolled on day 3 of illness and data will be collected for seven consecutive days. We seek to enroll a convenience sample of up to 100 consecutive patients with supratentorial sICH and acute ischemic stroke admitted to the Johns Hopkins Hospital Neurosciences Critical Care Unit (NCCU). Patients will be screened within 24-48 hours of arrival for eligibility according to the inclusion and exclusion criteria listed below. Informed consent will be obtained from the patient or legally authorized representative (LAR). The consenting process will be performed remotely via videoconference when possible.

Patients will be randomly assigned to the intervention plus usual care or usual care only group using a standard randomization schema generated by STATA 14.0 (College Station, Texas). The AIS and sICH cohorts will have separate randomization schemas.

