arterial line is not available the non-invasive cuff will be cycled every 5 minutes. Continuous vital signs will be extracted from the Sickbay software application, which collects physiologic data on all NCCU (see IRB00132987 Multimodality Neuromonitoring in the Neurocritical Care Unit). A clinician will observe the patient at all times during the session for signs of pain and discomfort and will administer the behavioral or visual analog pain scale every 5 minutes during the session depending on the patient's level of consciousness. Patient tolerance will be defined as the absence of the following: decline in neurological examination; sustained change in intracranial pressure, blood pressure, heart rate or oxygen saturation outside of prescribed goals per established patient specific plan of care; an increase in pain as measured by the behavioral pain scale or numeric pain rating scale not easily ameliorated by position change by the clinician; and accidental tube/device/catheter removal.^{22,34} Manual muscle strength testing using the Medical Research Council Sum Score will be performed by a clinician before the first session on days three and seven for patients in the control group. General strength will be assessed using a hand-held dynamometer for patients able to follow simple commands before the first session on days three and seven for patients in the control group. Other relevant covariates will be extracted from the medical record such as delirium screening, hospital acquired infections, volume of hematoma and cerebral edema on routine CT scans and body temperature.

The second control group, retrospective observational cohort, will consist of ischemic and hemorrhagic stroke patients admitted to the NCCU on the Johns Hopkins Hospital and Johns Hopkins Bayview campuses from March 16, 2020 through the end of the prohibition of tier II and III studies declared by the Johns Hopkins University Institutional Review Board. All data collection will be accomplished through retrospective chart abstraction. Face-to-face contact will not be required. The same clinical variables will be collected for this cohort to the extent that they are recorded in the medical record from admission to 90 days after the initial ischemic or hemorrhagic stroke.

The following samples will be obtained for the intervention + usual care group and the control group, usual care only:

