Usual care in the NCCU consists of evaluation and treatment by physical and occupational therapists assigned to the neurosciences service when an order for evaluation and treatment is entered by medical providers. Patients may be seen up to 5 times per week depending on their level of participation and intensity of therapy required, however many patients with sICH particularly those in coma are treated by therapists 2 times per week. Nursing staff in the NCCU provide passive range of motion and progressive a patient's mobility from supine to upright positioning, sitting at the side of bed, transferring to chair, lift assisted transfer to chair and ambulation as the patient's condition allows. All usual care activities will be recorded by the study team via extraction from the medical record. Usual care during the pandemic is similar to the care described above however, due to resource constraints it is possible that care focused on mobility and recovery was reprioritized in order to provide acute and intensive care for other patients.

Table 1. Study Activities Schedule for the intervention and prospective control group

	Admission day 1-2	Study day 1 = hospital day 3	Study day 2 = hospital day 4	Study day 3 = hospital day 5	Study day 4 = hospital day 6	Study day 5 = hospital day 7	Study day 6 = hospital day 8	Study day 7 = hospital day 9	Day of ICU transfer	30 days after hemorrhage (-10, +30 days)
Screening, Inclusion/Exclusion, Consent	X									
Intervention and monitoring										
Cycle ergometry 20 minute sessions (twice each study day)		XX								
Vital signs (BP, HR, RR, SpO ² , ICP)		X	X	X	X	X	X	X		
Pain scores		X	X	X	X	X	X	X		
Physiologic outcomes for the intervention and control groups										
Blood draw (IL1- β , IL-6, TNF- α , IL-10, CRP, BDNF)		X		X				X		
Saliva sample for cortisol		X		X				X		
CSF sampling, if a external ventricular		X		X				X		

drain is in place										
Outcome measures										
Medical Research Council Sum Score (strength testing) ²¹		X		X				X	X	X
Grip strength		X		X				X	X	X
Modified Rankin scale score	X								X	X
Barthel Index ¹²									X	X
Sunnybrook Neglect Assessment Procedure (SNAP) ³¹		X							X This battery will only be completed if the patient was found to have neglect on the initial assessment.	X This battery will only be completed if the patient was found to have neglect on the initial assessment.
Questionnaires										

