If a patient meets the following stopping criteria on >2 consecutive sessions the patient will be withdrawn from the study: change in neurological examination, sustained change in intracranial pressure, blood pressure, heart rate, or oxygen saturation that is outside of provider-prescribed range, significant pain exacerbated by mobilization.^{22,34}

g. Description of what happens to participants receiving therapy when study ends or if a participant's participation in the study ends prematurely.

Upon study procedure completion participants will continue to receive usual care.

4. Inclusion/Exclusion Criteria

Inclusion criteria:	Rationale:
Age \geq 18 years	Spontaneous intracerebral hemorrhage and acute ischemic stroke is typically a disease of the adult.
Supratentorial intracerebral hemorrhage with or without intraventricular hemorrhage	Only patients with a supratentorial ICH will be included due to the fact that patients with infratentorial ICH often require surgery, introducing an overlay of inflammation above that which is caused by the ICH itself. It is known that intraventricular hemorrhage increases severity of illness and mortality, however it is a common co-occurring process in patients with ICH and should be studied concurrently. ¹³
Acute ischemic stroke with a Medical Research Council Sum Score (MRCSS) of <27.	Patients with a clinical diagnosis of stroke and motor weakness as identified by the MRCSS as less than 27. ²¹
Pre-morbid modified Rankin Score of 0-2	The modified Rankin Score (mRS) is a commonly

	used tool to quantify disability after stroke and is scored from 0 to 6 with higher scores describing increased disability including death. The mRS will be used to characterize a patient's pre-morbid functional status correlating with a patient's potential for recovery after stroke as well as an outcome measure at discharge and 30 days after hemorrhage. ^{5,13} Patients with a mRS >2 prior to admission have poor potential for recovery.
Patient must be able to provide informed consent or have a legally authorized representative to provide consent on their behalf	
Exclusion criteria:	

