Aim 2: To determine the effects of twice-daily, lower extremity CE of 20 minutes duration plus usual care compared to usual care alone and a third retrospective cohort of patients receiving usual care during the COVID-19 pandemic on, the immediate and sustained physical impairment and disability scores at NCCU discharge and 30 days after hemorrhage.

Data from this aim will be analyzed in the same fashion as described above.

Hypothesis: The CE group will demonstrate decreases in 90-day modified Rankin Scale score, increases in the Medical Research Council sum score (muscle strength) and grip strength, less delirium positive days and hospital acquired infections.

d. Early stopping rules.

If a patient meets the following stopping criteria on >2 consecutive sessions the patient will be withdrawn from the study: change in neurological examination, sustained change in intracranial pressure, blood pressure, heart rate, or oxygen saturation that is outside of provider-prescribed range or significant pain exacerbated by mobilization.

6. Risks

a. Medical risks, listing all procedures, their major and minor risks and expected frequency.

The risks of this study are designed to be minimal. Potential risks to the participant include the following: hemodynamic instability, increased intracranial pressure, skin breakdown associated with the supine cycle ergometer, pain, muscle spasm and musculoskeletal injury.

b. Steps taken to minimize the risks.

Patients are continuously monitored on a cardiorespiratory monitor with oxygen saturation, heart rate, intracranial pressure (when applicable) and blood pressure, measured by arterial catheter or non-invasive cuff. Blood pressure, heart rate, oxygen saturation, respiratory rate and intracranial pressure will be measured and recorded continuously using the Medical Informatics, Sickbay software application currently installed in the NCCU and collecting data from all cardiorespiratory monitors. Pain will be measured and documented every 5 minutes visual analog scale or behavioral pain scale in patients unable to report pain level.

The NCCU is staffed 24 hours per day by a dedicated team of Neuro Intensivists, fellows and resident physicians assigned exclusively to the unit who can respond immediately to physiologic changes or adverse events when notified. A chain of command is followed when a primary provider is not available to respond due to other emergent patient care duties.

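### Aim 2's pandemic cohort is not tied to the trial's eligibility criteria or to entry on day 3, so its contrast with cycling can reflect selection; the 30-day and 90-day mRS also need reconciling

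*Combined protocol and SAP*

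**What the plan says.** Under Study Statistics, Aim 2 sets cycling plus usual care against concurrent usual care and against "a third retrospective cohort of patients receiving usual care during the COVID-19 pandemic on, the immediate and sustained physical impairment and disability scores". Outcomes are assessed at NCCU discharge and 30 days. Its analysis is one sentence that refers back to the method given for Aim 1.

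Section 3a defines the added group: "The second control group, retrospective observational cohort, will consist of ischemic and hemorrhagic stroke patients admitted to the NCCU" on two campuses, from March 16, 2020 until the research prohibition ends. The same clinical variables as in the trial are to be abstracted "to the extent that they are recorded in the medical record from admission to 90 days after the initial ischemic or hemorrhagic stroke". No size is given for this group.

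For the randomised patients, Section 3a names one campus and screening within 24-48 hours of arrival, and states: "Patients will be enrolled on day 3 of illness and data will be collected for seven consecutive days". Section 4 then restricts entry:

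- hemorrhage must be supratentorial;
- ischemic stroke must meet "Acute ischemic stroke with a Medical Research Council Sum Score (MRCSS) of <27";
- pre-morbid mRS must be 0-2;
- patients are excluded for GCS 3 at 48 hours, infection requiring antibiotics, or withdrawal of life support under consideration.

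The method in Study Statistics c compares baseline characteristics between the two groups and calls for an adjusted analysis if they differ. It allows parametric or non-parametric tests. For Aim 1 it specifies a two-sample t-test, or ANCOVA on the baseline outcome if that differs.

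The Aim 2 hypothesis names the 90-day mRS, MRC sum score, grip strength, delirium-positive days and hospital acquired infections.

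**The concern.** The randomised arms contain only patients who reached day 3 and passed Section 4. The pandemic cohort, as defined, starts at admission and has no such filter. The protocol's own rationale treats several of the excluded groups as prognostically different: it describes a pre-morbid mRS above 2 as carrying little prospect of recovery, and expects patients for whom withdrawal of life support is being considered to die around the time of randomisation. Infection at screening is excluded from the trial, yet hospital acquired infection is an Aim 2 outcome.

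A difference between cycling and pandemic care could therefore come from who was counted and from when. The pilot's stated purpose is to estimate effect size, so a biased estimate matters whether or not a test is significant.

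A smaller, separate matter is that Aim 2 is set at discharge and 30 days while its hypothesis rests on the 90-day mRS. The plan does not say which assessment answers the aim.

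**Working it through.** **1. The plan's own figure.** Inputs from Study Statistics c: effect size 0.28, power 80%, alpha 0.05. Two-sided, 1:1: n per arm = 2 × (1.960 + 0.842)² / 0.28² = 15.70 / 0.0784 ≈ 200.2, so 201 per arm and 402 in total, against 400 stated. The pilot fraction is 0.09 × 400 = 36, raised to 40 per stroke type, or 20 per arm. These figures are sound, but they concern cytokines in two arms and do not cover the pandemic cohort.

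**2. The two populations side by side.**

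| Item | Randomised arms | Pandemic cohort |
|---|---|---|
| Campuses | One | Two |
| Start | Day 3 | Admission |
| Section 4 | Applied at screening | Not mentioned |
| Hemorrhage site | Supratentorial only | Not restricted |
| Ischemic stroke severity | MRCSS <27 | Not restricted |
| Data | Prospective, Table 1 | Chart, as recorded |

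**3. What the adjustment can reach.** The adjusted analysis promised for differing baseline characteristics is the one described below that sentence, and the only one described is ANCOVA between two groups on the baseline outcome.

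- *mRS.* Table 1 schedules an mRS at admission day 1-2, so adjustment may be possible where the chart has it.
- *MRC score and grip.* Baseline values come from "Table 1. Study Activities Schedule for the intervention and prospective control group", which does not cover the pandemic cohort.
- *Delirium days and infections.* These counts have no baseline value.
- *Other covariates.* Section 3a lists items "such as delirium screening, hospital acquired infections, volume of hematoma and cerebral edema on routine CT scans and body temperature", but assigns none to a model.

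No baseline covariate removes patients who died before day 3 or who would have failed Section 4.

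**4. Direction.** Early deaths, deep coma, poor pre-morbid function and early infection in the pandemic cohort would favour cycling. Ischemic strokes with MRCSS of 27 or more, presumably milder, would favour pandemic care. The net direction cannot be fixed from the documents.

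**5. Illustrative size.** Assumptions, none given in the documents except n = 20: no cycling effect; outcome SD 1; 20 cycling and 40 pandemic patients; a share f of the pandemic cohort that would fail Section 4 or the day-3 condition, differing by D SD from the rest; unadjusted equal-variance t-test, two-sided 0.05; 40,000 simulated trials. The expected spurious shift is f × D.

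| f | Shift, D = 1 | Shift, D = 2 | False positives, D = 1 | False positives, D = 2 |
|---|---|---|---|---|
| 0 | 0 | 0 | 5% | 5% |
| 10% | 0.1 SD | 0.2 SD | 5.8% | 8.2% |
| 20% | 0.2 SD | 0.4 SD | 9.7% | 20.0% |
| 30% | 0.3 SD | 0.6 SD | 16.4% | 39.6% |

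At f = 20% the rates are 8.9% and 17.8% with 20 pandemic patients, and 10.3% and 21.2% with 80. The mRS is ordinal, so these figures are indicative only.

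**6. Time points.** Aim 2 and Study Statistics b give discharge and 30 days. Table 1 gives ICU transfer and 30 days (-10, +30), that is days 20 to 60, so a 90-day score falls outside it. Section 3b records the 90-day mRS for every patient and makes it the only outcome measure collected when no in-person visit is scheduled after discharge. The score is therefore planned data with no place in the outcome list or the schedule.

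**The case against.** The strongest reply is that the plan already has safeguards: an adjusted analysis when baseline characteristics differ, a choice of non-parametric tests, an admission mRS in Table 1, and relevant covariates taken from the chart. This stands in part. It would be wrong to infer that no adjustment is planned or that no covariate is named. The false-positive rates above assume no adjustment, so they overstate the problem wherever an effective adjustment is triggered. But the safeguards are worded for two groups, the only adjustment described is for the baseline outcome, and none replaces a missing eligibility filter or day-3 condition.

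Section 4 may also have been meant for everyone. It does not say so, the definition of the pandemic cohort does not cite it, and its consent criterion does not fit a chart review. If that was the intent, one sentence would settle it.

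Further, this is a secondary aim in a pilot, and Section 3a presents the third group as one of three care conditions, acknowledging that care may differ in the pandemic. That is fair and limits the weight of the point. It does not acknowledge that the patients may differ.

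A reader might also infer three stronger things that the documents do not support:

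- *A known excess of exposure time for delirium and infections in the pandemic cohort.* No start or end day for counting is set in any group, and counting from admission in all of them fits the text equally well.
- *A bias that must favour cycling.* The criteria pull both ways.
- *A 90-day mRS that will not be collected.* Section 3b collects it.

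**Conclusion.** The concern holds for the pandemic contrast only. As written, that contrast combines any effect of cycling with differences in eligibility, campus and survival to day 3, and the method applied by reference cannot separate them. It can show a difference in either direction when cycling does nothing. The randomised comparison of cycling with concurrent usual care is unaffected, so neither Aim 2 as a whole nor the trial is undermined.

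The documents do not give the size. The rates in the table rest on assumed values of f, D and the pandemic sample size and on an unadjusted test; they show that the distortion could matter, not that it will. The 30-day versus 90-day mRS needs no assumption, but it is a short reconciliation point. Overall this is a cheap improvement that should be made before the pandemic charts are analysed.

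**What to change.** 1. **Define the cohort.** Restrict it to patients alive and still hospitalised on hospital day 3, which Table 1 equates with study day 1, who meet the Section 4 criteria other than consent as far as the chart shows them. Requiring presence in the NCCU that day would go further than the rule for randomised patients. Report which criteria could not be applied. Count delirium days and infections from the same start day in all groups.
2. **Separate the analyses.** Keep randomised cycling versus usual care as the test of Aim 2. Still report all three care conditions, but give the pandemic cohort as a distinct non-randomised comparison within each stroke type. Adjust it for a short pre-named list, for example age, admission mRS where charted, and hematoma volume for hemorrhage. Add a sensitivity analysis limited to the Johns Hopkins Hospital campus.
3. **Reconcile the time points.** Add the 90-day mRS to Study Statistics b and Table 1, and state whether the 30-day or the 90-day score answers Aim 2.

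The cost is wording plus some extra chart abstraction to apply the criteria. The pandemic cohort will be smaller, some criteria such as MRCSS may not be charted, and 20 cycling patients per stroke type support few covariates. Confounding by unrecorded factors will remain, so the contrast should be described as observational.

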a. Primary outcome variable.

Pro-inflammatory cytokines: IL-1 β , TNF α , IL-6; Anti-inflammatory/repair factors: IL-10, BDNF

b. Secondary outcome variables will be measured at discharge and 30 days post-intracerebral hemorrhage or acute ischemic stroke.

- Modified Rankin Scale (mRS)
- Barthel Index will be measured at discharge and 30 days
- Medical Research Council Sum Score and dynamometry to measure muscle strength
- Discharge location (e.g., home, nursing facility), although not well studied, is commonly associated with physical function at discharge.
- SF-12
- Vital signs (e.g., heart, rate, blood pressure, respiratory rate)
- Delirium positive days
- Hospital acquired infections (e.g., catheter associated urinary tract infection and central line associated blood stream infection)
- CSF cytokines and repair factors
- Stroke Impact Survey

c. Statistical plan including sample size justification and interim data analysis.

Sample size was calculated for a fully powered trial and 9% of this sample size will be used for this pilot according to Cocks' methodology.¹⁰ An effect size of 0.28 was used, based on a published single group observational study in critically ill patients with a primary outcome of cytokine change.⁴⁷ Detection of an effect size of 0.28 with power of 80% and an α of 0.05 requires a sample size of 400 for a full trial and 9% represents a pilot sample size of 36 participants. Due to the enrollment of two stroke phenotypes, ischemic and hemorrhagic, we will analyze each cohort separately, therefore 40 participants per cohort are required. Accounting for attrition, up to 100 participants may be consented in order to enroll up to 40 participants per cohort. Each cohort will have 20 participants in each of two arms, intervention and control. It is estimated that at least 3-5 patients will be enrolled per month over 18 months.

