Descriptive statistics will be used to report sociodemographic variables. Baseline characteristics will be compared between the two groups. If they are found to be similar, post-intervention outcomes will be compared between the groups. If the baseline characteristics are found to be different, an adjusted analysis as described below will be conducted. Mean (SD) or median (IQR) will be used to describe continuous variables, and frequency (%) will be used for categorical variables. Mean differences in cytokines between the three time points (baseline, day 3 and day 7) will be calculated for each participant in the intervention and control groups. We will also plot data over time by group. Assumptions of normality will be checked and appropriate parametric or non-parametric tests will be used to detect absolute mean differences due to the small sample size, with an a priori significance level of 0.05, although the primary aim of this study is to estimate effect size. Data quality will be ensured by analyzing all samples in duplicate and procurement of samples will be performed by the same investigator. Statistical analysis will be performed using Stata 14.0 (College Station, Texas).

Primary aim (1): To determine whether a regimen of twice daily 20-minute sessions of CE plus usual care administered to patients with sICH and AIS (n=20) increases cytokines of the M2 phenotype and decreases cytokines of the M1 phenotype within 10 days of sICH when compared to a similar group of patients with sICH receiving usual care only (n=20).

The effect size, absolute difference between the two groups and the standard error of the difference will be estimated. The standardized difference will be estimated using Cohen's d. A two-sample t-test will be used to detect differences between post-test outcomes. If the baseline outcome is different, an analysis of covariance (ANCOVA) will be used to compare the outcomes between the two groups adjusting for the baseline difference as a covariate.

Hypothesis: Patients in the CE group will demonstrate an increase in cytokines of the M2 phenotype and a decrease in the M1 phenotype when compared to the group receiving usual care only.

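### Aim 2 borrows the cytokine analysis for ordinal, yes/no, count and categorical outcomes, so its effect estimates, baseline adjustment and handling of deaths do not fit those outcomes

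*Combined protocol and SAP*

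**What the plan says.** In the Combined protocol and SAP, Study Statistics part c, the analysis of Aim 2 reads: "Data from this aim will be analyzed in the same fashion as described above". What stands above it, under Primary aim (1), is the cytokine analysis. That analysis takes the absolute difference and its standard error, then "The standardized difference will be estimated using Cohen's d", then "A two-sample t-test will be used to detect differences between post-test outcomes". Adjustment is conditional: "If the baseline outcome is different, an analysis of covariance (ANCOVA) will be used to compare the outcomes between the two groups".

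The general paragraph of part c adds two things. For tests, "Assumptions of normality will be checked and appropriate parametric or non-parametric tests will be used to detect absolute mean differences". For description, "frequency (%) will be used for categorical variables". It also says that the study mainly aims to estimate effect size.

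The Aim 2 hypothesis names 90-day mRS, Medical Research Council (MRC) sum score and grip strength, together with "less delirium positive days and hospital acquired infections". Study Statistics part b also lists the Barthel Index and discharge location as secondary outcomes. Section 4 describes the mRS as a 0 to 6 scale whose scores include death.

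**The concern.** A method built for continuous laboratory values is carried over to outcomes of four other kinds: an ordinal scale with death at its end, an infection outcome (yes/no or a count), a count of days, and a set of categories. Four things follow.

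- **Effect measure.** A mean difference or Cohen's d is the only one named. For mRS and infection it is hard to interpret and to carry into a full trial, which is what a pilot estimate is for.
- **Discharge location.** No between-group method is given.
- **Baseline adjustment.** It rests on a baseline value of the outcome, which some outcomes lack.
- **Deaths.** Strength and Barthel scores do not exist for patients who have died, and the plan does not say how those patients enter the comparison.

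**Working it through.** **Inputs.** Study Statistics part c gives 20 per arm in each stroke cohort and a 0.05 level. The documents give no mRS distribution, infection rate or baseline correlation, so every such figure below is an assumption. The calculations cover the randomised two-arm comparison only.

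**The plan's own figure.** Per arm, n = 2(1.96 + 0.84)²/0.28² = 2 × 7.85/0.0784 ≈ 200.2, rounded up to 201, or 402 in total. The stated 400 reproduces, and 9% of 400 is 36. There is no sample size or power figure for Aim 2.

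**1. Does the t-test keep its level?** Four mRS distributions were assumed (percent at 0 to 6):

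- A: 2, 5, 10, 15, 28, 20, 20
- B: 20, 10, 5, 5, 15, 15, 30
- C: 0, 0, 3, 7, 25, 45, 20
- D: 0, 0, 0, 2, 5, 13, 80

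Over 40,000 simulated trials each, type I error was 0.046 to 0.050 for the t-test and 0.046 to 0.048 for the rank test. Power at a common odds ratio of 2.5 was 0.23 to 0.36 and 0.25 to 0.35 respectively.

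For a yes/no outcome with the same true rate in both arms, exact enumeration of the t-test gives:

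| True rate | 2% | 5% | 10% | 20% | 30% |
|---|---|---|---|---|---|
| Type I error | 0.001 | 0.012 | 0.039 | 0.050 | 0.053 |

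Test validity is therefore not the problem.

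**2. What does the mean difference say for mRS?** With 20 per arm, one patient moving one step changes the arm mean by 1/20 = 0.05. A move from 5 to death counts the same as a move from 1 to 2. Multiplying each cumulative odds by 2.5 in distribution A moves the mean from 4.02 to 3.22, a difference of 0.80. The variances are 2.32 and 2.56, so d = 0.805/√((2.32 + 2.56)/2) ≈ 0.52. The same steps for all four:

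| Distribution | Mean difference | Cohen's d |
|---|---|---|
| A | 0.80 | 0.52 |
| B | 1.21 | 0.52 |
| C | 0.49 | 0.49 |
| D | 0.30 | 0.39 |

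One and the same ordinal effect gives a fourfold range of mean differences.

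**3. What does Cohen's d say for infection?** For rates p and q, d = (q − p)/√((p(1 − p) + q(1 − q))/2).

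- 10% v 20%: 0.10/√((0.09 + 0.16)/2) = 0.28.
- 20% v 30%: 0.10/√((0.16 + 0.21)/2) = 0.23.

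Both are a 10-point risk difference, which d does not show.

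**4. Where is there a baseline?** Table 1 schedules MRC sum score and grip on study day 1, and mRS at admission. It schedules no Barthel Index before ICU transfer. Infections and delirium days accrue during the stay and have no baseline value, nor has discharge location.

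**5. What does conditional ANCOVA cost?** For an outcome with SD 1, the standard error of the difference is √(2/20) = 0.316. With baseline correlation 0.6, ANCOVA multiplies it by √(1 − 0.36) = 0.8, giving 0.253. For an assumed true d of 0.8 the ratio of effect to standard error is 0.8/0.316 = 2.53 unadjusted and 0.8/0.253 = 3.16 adjusted. If a baseline difference means p < 0.05, it arises in about 5% of randomised trials, so the rule nearly always returns the unadjusted test. In 40,000 simulated trials power was 0.70 for the t-test, 0.71 for the plan's rule and 0.86 for ANCOVA in all cases.

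**6. Deaths.** The mRS keeps every patient, with death as 6. MRC sum score, grip and Barthel can be scored only in survivors. Outcomes within one aim would then describe different sets of patients.

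**The case against.** The plan is more flexible than its named t-test. It checks normality, allows non-parametric tests and gives frequencies for categorical variables. The words about mean differences are loose, and a fair reader would accept a rank test for mRS or delirium days. This stands for the choice of test. It supplies no effect measure, and frequencies are descriptive only.

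A reader might infer that the t-test gives invalid results here. Step 1 does not support that.

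A reader might also infer that infections are rare and that the t-test would declare significance where an exact test would not. The documents give no infection rate and do not say whether infections are analysed as yes/no or as a count. The contrast also depends on the exact test chosen. For a hypothetical 0/20 v 4/20 the p-values are 0.036 (t-test), 0.106 (Fisher), 0.039 (Barnard) and 0.061 (Boschloo). For 1/20 v 6/20 they are 0.038, 0.091, 0.049 and 0.046. Most of the gap is Fisher's conservatism.

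A reader might infer that a t-test is planned for discharge location. That outcome is in the secondary list but is not named in Aim 2. What stands is that no between-group method is given for it anywhere.

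The survivor problem is not caused by the t-test, since a rank test on observed scores would share it. It belongs here because the one Aim 2 sentence is the only analysis plan for those scores.

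The Objectives and section 3a also call delirium and infections covariates, but part b and the Aim 2 hypothesis treat them as outcomes.

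**Conclusion.** The point holds as a problem of estimation and specification, not of test validity. The mean difference and Cohen's d are poor effect measures for mRS and infection. Discharge location has no between-group method. The ANCOVA clause cannot apply to infections, delirium days or Barthel. Strength and Barthel comparisons would use survivors only, without saying so.

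The two sizes are the 0.30 to 1.21 range of mean mRS differences for one odds ratio, and power of 0.71 against 0.86 for a strength score. The first rests on four assumed distributions and proportional odds. The second rests on d = 0.8, a correlation of 0.6, normal data and a 0.05 rule for baseline difference. At the plan's own d of 0.28, with the same correlation, power is low either way (about 0.13 against 0.19). These are secondary outcomes in a pilot, so severity is modest.

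**What to change.** Replace the Aim 2 sentence with methods by outcome type:

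- **mRS:** proportional-odds model, or Wilcoxon test with a generalised odds ratio, with death as 6, adjusted for pre-morbid mRS.
- **Infection:** define it as yes/no and report the risk difference with an exact interval.
- **Delirium days:** rank or count analysis.
- **Discharge location:** ordered categories that include death.
- **MRC sum score and grip:** ANCOVA on the study-day-1 value in all cases, whether or not baseline differs.
- **MRC sum score, grip and Barthel:** add a rank analysis that places deaths worst, and report the number of deaths per arm. Section 3b collects only the 90-day mRS from patients without an in-person visit. Those missing scores are not deaths and should be counted separately.

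The cost is plan wording only. All these data are already scheduled or taken from the record, and no patient or visit is added. It is a free improvement.
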